#### 8.11.1.2 Intensity of the adverse events

The intensity of an AE can be Mild (tolerable), Moderate (interferes with daily activates), Severe (daily activities impossible). If intensity is missing, it will be considered Severe for the analysis.

#### 8.11.1.3 Adverse event leading to premature treatment discontinuation

An adverse event that led to the permanent discontinuation of study treatment is an AE with the 'Action taken with study drug' marked as 'Drug discontinued' in the CRF section "Adverse Event".

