5.6 Withdrawal from Study

Subjects may be withdrawn at any time. Once dosing has occurred, every attempt should be made to continue assessments to ensure the safety of the subject. Specific reasons for withdrawing a subject should be documented in the eCRF, and include, but are not limited to:

- Subject's decision
- The Investigator or Sponsor judges that it is in the best interest of the subject to stop study treatment due to any abnormality compromising subject safety
- Pregnancy
- Severe noncompliance to the study protocol as judged by the Investigator and/or the Sponsor.

Subjects who prematurely discontinue may be replaced, per Sponsor decision. Subjects will not be allowed to re-enter the study.

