7.8 Documentation

All adverse events occurring after the subject has signed the informed consent will be fully recorded in the subject's eCRF. Each event will be described in detail, along with start and stop dates, severity, relationship to IMP, action taken and outcome.

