### **8.6 COMPLIANCE WITH STUDY TREATMENT**

The IMP will be administered at the clinic under supervision of study personnel (i.e., the Investigator or delegate) and cannot be provided to the subjects to take home.

Compliance with treatment (%) will be always 100% if treatment is administered at each visit (12 in total), from Week 1 D1 to Week 6 D40.

Study treatment is considered administered if answered 'Yes' to the question "LSD / Placebo administered?" in the "Study Drug Administration" CRF section. Study drug administration will be collected at each visit.

If Compliance with treatment (%) is different from 100%, it will be derived according to the following formula:

Total compliance (%) = (Total number of doses taken / Total number of expected doses) x 100\*,  
where:

*Total number of doses taken = Total number of expected doses – Total number of missed doses.*

*Total number of expected doses = 12 (number of doses to be administered at all 12 visits).*

*Total number of missed doses = number of doses not administered (study treatment is considered NOT administered if answered 'No' to the question "LSD / Placebo administered?" in the "Study Drug Administration" CRF section).*

In case of “Special Situation” at any visit (answer to “Were there any special situation with the study drug?” is [Yes]), the compliance will be not calculated, and the following information will be provided:

- Number of subjects with at least one Special Situation;
- Number of Special Situations;

and number of patients with ticked box 'Yes' to any of the following:

- Medication error or incorrect drug administration;
- Overdose (exceeds the protocol-specified maximum);
- Deliberate abuse;
- Deliberate misuse;
- Drug interaction;
- Occupational exposure.

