#### 10.7.2.1.1 *Definition of intercurrent events (IEs)*

1. IEs related to COVID-19 pandemic are confirmed if:

- AE term AEDECOD is 'SARS-CoV-2 test positive' in the sdtm database. The AE start date AESTDTC will be considered to assign missing values (as defined in bullet 1 of Section 10.7.2.2) to all assessments following this date and up to and including Week 6 D40.

2. Intake of prohibited medications/therapies defined in APPENDIX C will be finalized and flagged accordingly on a case-by-case basis by a Sponsor medical review of the concomitant medications as defined in Section 8.4.3. The CM start date will be considered to assign missing values (as defined in bullet 2 of Section 10.7.2.2) to all assessments following this date and up to and including Week 6 D40.
3. Other IEs leading to treatment/study discontinuation (except those related to COVID- 19 pandemic) are confirmed if:

the action taken AEACNOTH of the corresponding adverse event is 'DRUG DISCONTINUED' or 'SUBJECT WITHDRAWAL' in the sdtm database and subject had study assessments after the AE onset date AESTDTC and up to and including Week 6 D40.

In all cases if the date of the assessment and the IE start date occur in the same date, this assessment values will be assigned to missing.

If the date of assessments following the IE start date are missing, these will be imputed based on the theoretical date the assessments should have been occurred:

- if the IE start date <= study day 9 then both Week 2 and 6 assessments have to be set to missing and imputed
- if the IE start date is between study day 10 and 44 then Week 6 assessment has to be set to missing and imputed

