#### **10.12.1.1 Subgroup analysis**

TEAEs, SAEs, AEs related to the study drug and AEs leading to premature treatment discontinuation will be tabulated on SAF by preferred term (PT) by treatment phase as follows:

- **Days of dosing:** all AEs occurred on same date/visit of treatment but only during or after administration of study drug (with time on or after treatment administration). Week 1 D1 (Dose 1), Week 1 D5 (Dose 2), Week 2 D8 (Dose 3), Week 2 D12 (Dose 4), Week 3 D15 (Dose 5), Week 3 D19 (Dose 6), Week 4 D22 (Dose 7), Week 4 D26 (Dose 8), Week 5 D29 (Dose 9), Week 5 D33 (Dose 10), Week 6 D36 (Dose 11), Week 6 D40 (Last dose 12);

This information will be pooled in summary table, i.e. all AEs occurred on/after all doses: first, second etc. until last dose; as well as will be summarized separately, i.e. AEs occurred on/after each dose: on/after first dose, on/after second dose etc. and until on/after last dose.

- **Non-dosing days:** (a) all AEs with the date different from treatment administration date/visit defined above and until Week 10 Follow-up visit. (b) all AEs which occurred prior to study drug administration (with time before administered dose) on dosing days.

This information will be pooled in summary table, i.e. all AEs occurred between doses: first and second, second and third etc. until Week 10 Follow-up visit (EOS) or until Early Termination (ET) whatever comes earlier, as well as will be summarized separately, i.e. split by periods between doses: Dose 1 - Dose 2, Dose 2 - Dose 3, Dose 3 - Dose 4, Dose 4 - Dose 5, Dose 5 - Dose 6, Dose 6 - Dose 7, Dose 7 - Dose 8, Dose 8 - Dose 9, Dose 9 - Dose 10, Dose 10 - Dose 11, Dose 11 - Dose 12, Dose 12 | last administered Dose - EOS | ET.

In case of missing dates, the rules defined in Section 11.3.3 will be applied. In case of missing time of the AE or the treatment administration on the same day, the AE will be considered as occurred after the treatment administration, meaning will be summarized in 'Days of dosing' category.

Frequency statistics will be presented by treatment group. The summary tables will be presented in descending order according to their incidence in the active treatment group of 'Days of dosing' treatment phase (e.g., individual preferred term with the highest number of occurrences appear first) sorting ties alphabetically.

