### 13.2.11 Layout L10

Study MMED007 - Deliverables: <Deliverables>

Listing <Number of listing>

<Title>

Analysis set: <analysis set>

Subject ID	Active Treatment	System organ class/ Preferred term/ Reported term	Start date/ Time/ Study Day*	End date/ Time/ Duration (days)	Treatment Emergent**	Serious	Severity	Relation. to study drug	Action Taken With Study drug		Outcome
									With Study drug	Outcome	
xxx	xxx	xxxxxx/ xxxxxx/ xxxxxx	ddmmyy/ yyy/ Hh:mm	ddmmyyyy/ Hh:mm	Yes/No	No/Yes: xxxx	xxxx	xxxx	xxxx	xxxx	xxxx

\*Study day is the day of the event relative to the treatment start date.

\*\*Treatment-emergent adverse event is any event with onset date/time between the study treatment start date and the study treatment end date, limits included.

System Organ Class and Preferred terms are based on MedDRA 25.1 dictionary.

Program: [program\\_name.sas](#), Produced on yyyy-mm-dd hh:mm (CET),

Snapshot date: yyyy-mm-dd, Draft/final

Page x of x

*Note for Programmer: Severity = Intensity of AE.*

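### SAP 8.11.1.3 recognises an adverse event that ended treatment by one action code only, so an event coded only as subject withdrawal before dose 12 could drop out of four safety outputs

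*SAP*

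**What the plan says.** The safety definition is in SAP 8.11.1.3. An adverse event that permanently ended study treatment "is an AE with the 'Action taken with study drug' marked as 'Drug discontinued' in the CRF section" for adverse events. No other code is mentioned.

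The estimand section uses two codes. Under SAP 10.7.2.1.1 item 3, an intercurrent event leading to treatment or study discontinuation is confirmed if "the action taken AEACNOTH of the corresponding adverse event is 'DRUG DISCONTINUED' or 'SUBJECT WITHDRAWAL" and if the "subject had study assessments after the AE onset date AESTDTC and up to and including Week 6 D40".

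Four planned outputs present adverse events that led to stopping study drug: AEPDSOC, AEPDPT and LAEPD (SAP 12.8.1) and AEPDPTTP (SAP 12.8.1.1). Nothing in the SAP carries the withdrawal code into any of them.

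On dosing, SAP 8.6 has study drug given under supervision, "and cannot be provided to the subjects to take home", and Protocol 5.5 says the same. The twelfth and final dose is due at "Week 6 D40 (Last dose 12" in the dose list of SAP 10.12.1.1). Among the reasons for withdrawing a subject from the study, Protocol 5.6 includes a judgement that it is "in the best interest of the subject to stop study treatment due to any abnormality compromising subject safety".

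**The concern.** Within one SAP, the safety section recognises one action code and the estimand section recognises two. An investigator who takes a subject out of the study because of an adverse event could reasonably choose the withdrawal code. If that is the only code recorded, 8.11.1.3 does not see the event, although treatment ended because of it.

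Safety and tolerability by adverse-event assessment is a secondary objective (SAP 7.2), and these four outputs are the ones dedicated to adverse events that stopped treatment. The termination reasons in SAP 8.7 are loss to follow-up, death, COVID-19 and a free-text other, so the disposition tables have no adverse-event category to supply the count. Any omission would make the drug look better tolerated in whichever arm it occurred.

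**Working it through.** The plan gives no figure to reproduce here. The check is mainly a comparison of texts, with some small arithmetic.

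**1. The two definitions**

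| | SAP 8.11.1.3 | SAP 10.7.2.1.1 item 3 |
|---|---|---|
| Purpose | Safety outputs | Primary estimand |
| Field named | CRF label for action taken with study drug | SDTM variable AEACNOTH |
| Codes accepted | *Drug discontinued* | *Drug discontinued*, *Subject withdrawal* |
| Further condition | None | Assessments after onset, up to Week 6 D40 |

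Item 3 is used here only to show that the second code exists. An estimand rule may properly be wider than a safety rule.

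**2. Does withdrawal before dose 12 end treatment?** Yes. Study personnel give every dose and there is no home supply. Protocol 5.6.1 directs subjects who withdraw after dosing to the end-of-study assessments.

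**3. One field or two?** The annotated CRF would settle this, but it is not among the documents. Three things suggest one field. *Drug discontinued* is a value in both sections. Listing layout L10 has a single action column, "Action Taken With Study drug". Protocol 7.8 names the item once per event, in the run "severity, relationship to IMP, action taken and outcome". None of these is proof. The possible cases for an adverse-event withdrawal before dose 12 are:

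| Data structure | What is recorded | Captured by 8.11.1.3? |
|---|---|---|
| One field | *Subject withdrawal* | No |
| Two fields | Both codes | Yes |
| Two fields | *Subject withdrawal* only | No |

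**4. Size.** With k missed subjects in a planned arm of 26, the reported rate is too low by 100 × k / 26 percentage points. The values of k are assumed:

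- k = 0: 0
- k = 1: 3.8
- k = 2: 7.7
- k = 3: 11.5

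**5. Why the added code needs a dose condition.** SAP Table 3 puts dose 12 at Day 40 and the follow-up visit at Day 70. From Day 1 to Day 70 is 69 days, of which 70 − 40 = 30 come after dose 12, and 30/69 = 43%. A withdrawal in that stretch misses no dose and must not count. The 43% is a share of calendar time, not of expected withdrawals.

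**6. Why it also needs an onset condition.** Take a subject who stops dosing for a non-medical reason from dose 9 (due Day 29), then has an adverse event on Day 35 coded *Subject withdrawal*. Dose 12 was not given, but the event did not end treatment. Requiring onset before Day 29, the due date of the first dose in the final run of missed doses, excludes it. Onset on Day 27 would be counted. A subject who misses dose 11 but receives dose 12 has no final run of missed doses and is not counted.

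**The case against.** The strongest objection is that everything turns on a form we cannot see. 8.11.1.3 quotes a CRF label and item 3 quotes a differently named SDTM variable. Withdrawing a subject is not an action with the drug, so L10's column heading fits a separate withdrawal field at least as well. *Drug discontinued* under AEACNOTH could be loose drafting. Protocol 5.6 also speaks of stopping treatment, and an investigator doing that might well mark *Drug discontinued*. This stands in full as a limit on certainty. It does not remove the point. No text requires both fields to be filled in, and adding the code counts nobody extra if every such event already carries *Drug discontinued*.

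A second objection is that the rules need not match. Item 3 covers treatment or study discontinuation, whereas 8.11.1.3 concerns study drug only. That is correct. A reader might infer that the SAP contradicts itself, and the documents do not support that. The argument here is narrower: in this trial, leaving before dose 12 is also leaving treatment.

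Third, the event is not lost. It stays in the full listing LAE, where a single action field would print the withdrawal code beside it, and layout T7 has a sub-row under *Other* for a specified reason. This also stands, and it is why the point is minor. Neither place gives a count of such events by preferred term and arm.

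**Conclusion.** The point holds conditionally. If the two codes are alternatives in one field, or if only the withdrawal code is filled in, an adverse-event withdrawal before dose 12 is left out of AEPDSOC, AEPDPT, AEPDPTTP and LAEPD. With two fields, both completed, the current rule already works.

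A reader might go further and conclude that these outputs will under-report treatment stops. The documents do not support that. The coding structure is suggested rather than shown, and the number of affected events may be zero. The 3.8 percentage points per subject assumes 26 subjects in the arm's safety set.

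The correction is worth making but small. None of the four outputs is marked as a key deliverable in SAP 12.8, and Protocol 13.6.7 plans no inference on safety. The primary and key secondary analyses do not use 8.11.1.3.

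**What to change.** Check the annotated CRF (listed in SAP 2.2) for whether one or two fields are involved. Then amend 8.11.1.3 along these lines:

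- Keep every adverse event marked *Drug discontinued*, with no added condition. A derived dosing check should not override what the investigator recorded directly.
- Also count an adverse event whose action taken, in either field, is *Subject withdrawal* when both of these are true: dose 12 was not administered; and the event began on or after the first dose and before the due date of the first dose in the final unbroken run of missed doses.
- Use this definition in AEPDSOC, AEPDPT, AEPDPTTP and LAEPD. Leave T2 and T7 as planned from the Termination Form.

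Test the last dose itself, not whether any dose was missed: a subject who misses dose 11 and receives dose 12 has not stopped.

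The cost is a short addition to 8.11.1.3 and a few program conditions. The action codes, the onset date and the per-visit dosing question (SAP 8.6) are already in the data, and no table layout changes. The one downside is that the reported rate of adverse-event discontinuation may be slightly higher.

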#### 8.11.1.4 AEs related to study drug

An AE is considered related to study drug if the tick box "Relationship to the study drug" is marked as "Definitely Related" or "Probably Related" or "Possibly Related" in the "Adverse Event" CRF section.

### ***8.11.1.5 Unexpected Adverse Reaction (UAR)***

When the outcome of an adverse reaction is not consistent with the applicable product information, this adverse reaction should be considered as an Unexpected Adverse Reaction (UAR). Information on UAR will not be included in the CRF but the sponsor will provide expectancy/unexpectancy details.

### ***8.11.1.6 Suspected Unexpected Serious Adverse Reaction (SUSAR)***

Suspected Unexpected Serious Adverse Reaction (SUSAR) is any suspected adverse reaction related to an IMP that is both unexpected and serious (expectancy/unexpectancy details will be provided by the Sponsor).

### ***8.11.1.7 Serious Adverse Event (SAE)***

An AE is considered serious if the question 'Is the event serious?' in the CRF section "Adverse Event" is marked as 'Yes'.

### ***8.11.1.8 Serious Adverse Reaction (SAR)***

A Serious Adverse Reaction (SAR) is a SAE that is determined to be related to the study treatment. That is, SAEs that are determined to have a causal relationship of "Possibly Related", "Probably Related" or "Definitely Related" on the 'Relationship to study drug' category of the 'Adverse Events' CRF section will be considered SARs.

## **8.11.2 Death**

The date and the cause of death occurred during the study are derived from "Adverse Event" section of the CRF.

## **8.11.3 Laboratory**

A routine laboratory blood test will be performed at the screening examination, and similarly during follow-up visits: Week 2, Week 4, Week 6 and Week 10 (see Section 2.1.2).

In particular, the laboratory parameters are the ones listed below:

### ***8.11.3.1 Hematology***

- Hemoglobin;
- Hematocrit;
- MCV;
- MCH;
- Platelet count;
- Red blood cell count;
- White blood cell count (including Basophils, Eosinophils, Lymphocytes, Monocytes, Neutrophils).

### ***8.11.3.2 Chemistry***

- Albumin;
- Total protein;
- Alkaline phosphatase;
- ALT;
- AST;
- Bilirubin, total;
- Chloride;

- Creatinine;
- Creatinine clearance (CKD-EPI);
- FSH (follicle stimulating hormone);
- GGT (gamma-glutamyl transferase);
- C Reactive Protein;
- Glucose;
- Lactate dehydrogenase;
- Blood urea nitrogen or urea;
- Phosphate;
- Potassium;
- Calcium;
- Sodium.

In addition, a [REDACTED] and a urine pregnancy test, only in women, will be performed at selected time points (Baseline, Week 2, Week 4, Week 6, Week10) before IP dosing throughout the study (see Section 2.1.2).

The definitions of marked abnormalities in SI units are provided in Table 5 and Table 6 below.

The columns labelled "L", "LL", "H" and "HH" display the increasing grade (severity) of abnormally low ("L", "LL"), or high values ("H", and "HH") for each of the laboratory parameters listed in the first column, as appropriate.

Treatment-emergent MLAs are those occurring after the study treatment start and up to study treatment discontinuation, that were not present at baseline in the same or worse category (considering the direction of worsening). In other words, the MLAs are evaluated independently by direction of worsening (e.g., a post-baseline MLA of "HH" is considered treatment-emergent if the baseline is "L" or "LL" (where applicable) or "H", or within normal limits or missing. On the other hand, it is not considered as treatment-emergent if the baseline is "HH" when applicable).

**Table 5. Abnormal laboratory values: Hematology (SI units)**

Laboratory test name (CDISC Synonym[s])	L	LL	H	HH
Hemoglobin	<100 g/L	<80 g/L	>20 g/L above baseline	>40 g/L above baseline
Hematocrit; EVF; Erythrocyte Volume fraction; PCV; Packed Cell Volume (male)	<0.32 L/L	<0.20 L/L	>0.60 L/L	>0.65 L/L
Hematocrit; EVF; Erythrocyte Volume fraction; PCV; Packed Cell Volume (female)	<0.28 L/L	<0.20 L/L	>0.55 L/L	>0.65 L/L
MCV	< 82 fl	NA	> 98 fl	NA
MCH	< 27 pg	NA	> 33.2 pg	NA
Platelets (assuming no platelet cluster)	<75 x 10  /L	<50 x 10  /L	>600 x 10  /L	>999 x 10  /L

Red Bloodcell count (RBC)* / Erythrocytes (10  /L)				
Male	4.60/pl / 10  /L	4.1/pl / 10  /L	6.10/pl / 10  /L	6.3/pl / 10  /L
Female	3.90/pl / 10  /L	3.5/pl / 10  /L	5.20/pl / 10  /L	5.5/pl / 10  /L
Leukocytes; White Blood Cells	<3.0 x 10  /L	<2.0 x 10  /L	>20.0 x 10  /L	>100.0 x 10  /L
Granulocytes PLUS Neutrophils Band Form*	NA	NA	>90%	>95%
Monocytes				
Male	< 5% < 5%	NA	> 12% > 13%	NA
Female		NA		NA
Basophils	NA	NA	≥ 1.5%	NA
Neutrophils (Abs)	<1.5 x 10  /L	<1.0 x 10  /L	NA	NA
Eosinophils (Abs)	NA	NA	>5.0 x 10  /L	NA
Lymphocytes (Abs)	<0.8 x 10  /L	<0.5 x 10  /L	>4.0 x 10  /L	>20 x 10  /L

\*Red Bloodcell count (RBC)\* in pl should be used in all summaries and listings

**Table 6. Abnormal laboratory values: Blood chemistry (SI units)**

Laboratory test name (CDISC Synonym[s])	L	LL	H	HH
Alanine Aminotransferase; SGPT	NA	NA	> 3x ULN	> 5x ULN
Aspartate Aminotransferase; SGOT	NA	NA	> 3x ULN	> 5x ULN
Gamma Glutamyl Transferase	NA	NA	> 2.5x ULN	> 5x ULN
Alkaline Phosphatase	NA	NA	> 2.5x ULN	> 5x ULN
Bilirubin; Total Bilirubin	NA	NA	> 2x ULN	> 5x ULN
Creatinine	NA	NA	> 1.5x ULN	>3x ULN
Glucose (Non-diabetic Fasting)	<3.0 mmol/L	<2.2 mmol/L	>8.9 mmol/L	>13.9 mmol/L
Sodium	NA	<130 mmol/L	>150 mmol/L	>155 mmol/L
Potassium	<3.2 mmol/L	< 3.0 mmol/L	>5.5 mmol/L	>6.0 mmol/L
Creatine Kinase	NA	NA	>5x ULN	>10x ULN
Urate; Uric Acid	NA	NA	> 590 µmol/L	>720 µmol/L
Albumin	<30 g/L	<20 g/L	NA	NA
Total Protein	<66 g/L	NA	> 87 g/L	NA
Chloride	< 98 mmol/L	NA	>107 mmol/L	NA
Lactate dehydrogenase	NA	NA	≥ 250 U/L	NA
Creatinine Clearance	<60 ml/min	<30 ml/min	NA	NA
Blood Urea Nitrogen; Urea Nitrogen	NA	NA	>2.5x ULN	>5x ULN

#### **8.11.4 Vital signs**

Vital signs (supine blood pressure (mmHg), body temperature (°C), respiratory rate (breath/minute), heart rate (bpm)) will be measured at each visit (Section 2.1.2) and collected in the "Vital Signs" section of the CRF.

Refer to section 11.1.1.8 for definition of the Baseline. In case of missing time of the Vital Signs assessment on the date of first dosing, please input time 00:00 on the corresponding date.

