6.2.3. Day 1 dosing (\pm 1 day)

Randomization to MM-120 or placebo will occur before the first dose on Day 1. The first dose must be administered in the clinic. For this visit, the subject will remain at the testing facility for 6 hours after drug administration for blood sampling and getting familiar with the effects of LSD.

Study activities performed before dosing:

[REDACTED] vital signs, pregnancy test, C-SSRS (Since Last Visit), record adverse events and concomitant medications, check daily diary.

Study activities performed after dosing:

Blood samples for PK are taken repeatedly at 0, 0.5, 1, 2, 3, 4, 6 hours after dosing. Pharmacodynamics are measured over 6 hours including subjective effects as assessed using VAS scales, blood pressure and heart rate. 12-lead ECG will be performed at 2 hours post dosing. The 5D-ASC and MEQ30 are assessed 6 hours after dosing.

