### **2.1.3 Visit windows**

As subjects do not always adhere to the protocol visit schedule, the following rules will be applied to assign actual visits to analysis visits for all parameters.

The visit windows and the target days for each visit (including unscheduled ones) are listed below in Table 2. The reference day is Day 1, the first day of dosing, as defined in Section 11.1.1. If a subject has two or more actual visits in the same visit window, the visit closest to the target day will be used for recording data from that visit in the EDC. The data collected scheduled and unscheduled visit(s) will be mapped to visits as follows: If two actual visits are equidistant from the target day within a visit window, the later visit will be used; if more than one value falls on the same day then the last sequential number in sdtm will be used.

All assessments corresponding to both scheduled and unscheduled visits will be included in subject listings.

Table 2 contains analysis visit windows and the target study days for the following selected visits: Baseline, Week 2, Week 4, Week 6 and Week 10; lower and upper limits associated with each visit will cover all possible days from randomization to end of study allowing mapping all the applicable assessments to the visits.

As vital signs and Columbia-Suicide Severity Rating Scale (C-SSRS) will be evaluated at each visit (twice weekly), a different time windowing will be applied to those variables only (see Table 3). Daily diary contains daily sleep quality/ duration rating assessments that will be computed at each week by the mean of values recorded between lower and upper limits (days) specified in Table 4, no target study day will be considered.

For parameters, where Time Interval Upper Limit for Baseline is equal to 1, please apply a rule of time defined in section 11.1.1.8 for Baseline.

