### **11.1.1.8 Baseline value**

Except where otherwise specified, baseline is defined as the last value measured or assessed before or on the date of the first dose of investigational drug administration at Visit 1. If the baseline visit takes place on the date of the first dose of investigational drug, then time should be considered, i.e. baseline date/time < first dose date/time.

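### The SAP stamps any untimed Day 1 vital-sign record 00:00 without limiting this to pre-dose records, so in narrow circumstances a post-dose reading can become a subject's vital-sign baseline (minor).

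*SAP*

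**What the plan says.** **Imputation.** SAP 8.11.4 (Vital signs) points to 11.1.1.8 for baseline and then adds: "In case of missing time of the Vital Signs assessment on the date of first dosing, please input time 00:00 on the corresponding date."

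**Baseline.** SAP 11.1.1.8: "baseline is defined as the last value measured or assessed before or on the date of the first dose of investigational drug administration". If that falls on the dosing date, "then time should be considered, i.e. baseline date/time < first dose date/time".

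**Which parameters follow the time rule.** SAP 2.1.3: "For parameters, where Time Interval Upper Limit for Baseline is equal to 1, please apply a rule of time defined in section 11.1.1.8". SAP Table 3 sets that upper limit at Day 1 for vital signs. Its next window opens on Day 2.

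**Several values on one day.** SAP 2.1.3: "if more than one value falls on the same day then the last sequential number in sdtm will be used".

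**Day 1 measurements.** Protocol 6.2.3 lists, among the activities before dosing, "vital signs, pregnancy test, C-SSRS (Since Last Visit), record adverse events and concomitant medications, check daily diary". After dosing it says: "Pharmacodynamics are measured over 6 hours including subjective effects as assessed using VAS scales, blood pressure and heart rate". Protocol 6.2.2 and the schedule of events also place vital signs at the Day -1 Baseline visit.

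**Use of the baseline.** SAP 10.12.2 lists and summarises vital signs and their changes from baseline on the safety set.

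**The concern.** Table 3 has no Day 1 post-dose slot, so any Day 1 record in the vital-signs data falls in the baseline window. Only the time test keeps a post-dose reading out of the baseline. Giving 00:00 to every record without a time switches that test off for exactly the records whose position relative to the dose is unknown.

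If a post-dose reading is taken as baseline, the subject's later changes in that parameter are measured from a value that may include an acute drug effect. Both arms can be misassigned, but only MM-120 readings can carry such an effect, so a rise in that arm would tend to be understated.

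The rule also runs opposite to the SAP's own convention elsewhere. In 10.12.1.1, an adverse event on a dosing day with a missing event or dosing time is counted as post-dose.

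**Working it through.** The plan gives no figure to reproduce. The check applies the rules to the possible Day 1 record patterns.

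**Rules applied**
1. An untimed Day 1 vital-sign record gets 00:00 (8.11.4).
2. A record is eligible as baseline if it is before Day 1, or on Day 1 with "baseline date/time < first dose date/time" (11.1.1.8).
3. Among eligible records, take the last value by time (11.1.1.8). Equal times go to the last sequence number (2.1.3).
4. As an alternative to step 3, let the same-day sequence rule in 2.1.3 decide outright.

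**Assumptions.** The dose is at 10:00 (any time after 00:00 gives the same result), a timed Day -1 record exists, and sequence numbers follow the order of measurement. The documents do not confirm the last assumption.

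| Pattern | Day 1 pre-dose | Day 1 post-dose | Baseline, 11.1.1.8 governs | Baseline, 2.1.3 sequence rule governs |
|---|---|---|---|---|
| A | timed | untimed | pre-dose | **post-dose** |
| B | untimed | untimed | **post-dose** | **post-dose** |
| C | missing | untimed | **post-dose** | **post-dose** |
| D | untimed | timed | pre-dose | pre-dose |
| E | timed | timed | pre-dose | pre-dose |

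- In B both records become 00:00, both pass the time test, and the tie goes to the later sequence number.
- In C the post-dose record at 00:00 on Day 1 is later than the Day -1 record and displaces it.
- In A the timed pre-dose reading is later than 00:00 and protects the baseline, unless the sequence rule is read as overriding 11.1.1.8. The SAP does not state the precedence. However, 2.1.3 itself sends parameters with a Day 1 upper limit to the time rule, so 11.1.1.8 is the more natural reading.
- In D and E the rules give the right answer.

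**Size.** Change is the later value minus baseline (SAP 11.2.2). If the baseline is too high by r, each later change for that subject is too low by r. With k affected subjects among n in the arm, the arm mean change is off by (k/n) × r. Neither k nor r is in the documents, so this cannot be turned into a figure.

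**The case against.** The strongest reply is that the trigger may never arise. SAP 8.11.4 concerns data from the Vital Signs CRF section. Protocol 6.2.3 lists vital signs before dosing and puts the post-dose blood pressure and heart rate under pharmacodynamics. Listing L26 prints systolic, diastolic and heart rate beside the plasma concentrations, by planned time point and with clock times. Listing L11, for vital signs, has no time-point column. If the post-dose readings are held only with the PK samples, an untimed Day 1 vital-sign record is normally the pre-dose one, and 00:00 classifies it correctly. This is plausible, but the documents do not settle it, and 8.11.4 does not say it.

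SAP 2.1.2 also requires date and time for every measurement, so untimed records should be uncommon. That stands.

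A reader might infer that the rule hides the acute cardiovascular effect which the repeated Day 1 readings are meant to document (Protocol 7.4.1). The documents do not support that. Table 3 has no Day 1 post-dose visit, so the change table never shows the acute effect whatever the baseline. L26 lists the Day 1 readings as absolute values, which the choice of baseline does not touch.

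A reader might also put a mmHg figure on the bias. Protocol 1.4.3 reports no relevant blood pressure or heart rate change at 20 µg. The tie rule would pick the latest reading, near 6 hours, whereas the maximum subjective effect is at 2.3 hours and effects last about 6 hours. Any figure would be assumption only.

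Finally, a filter on planned time point may not be available for vital signs, since L11 shows no such field. The fix therefore needs a fallback.

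**Conclusion.** The wording gap is real and minor. As written, the rules select a post-dose baseline when an untimed post-dose reading is in the vital-signs data and the Day 1 pre-dose reading is either missing (pattern C) or also untimed and sequenced earlier (pattern B). In both, a valid Day -1 value is passed over.

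The conclusion rests on post-dose readings being in the vital-signs data, which is not shown, and, for pattern B, on sequence numbers following measurement order. Frequency and size cannot be stated.

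It would be too strong to say that all later safety changes are affected. The effect is confined to that subject's changes in that vital-sign parameter; laboratory and ECG baselines are untouched. It would also be too strong to say that a timed pre-dose reading is generally displaced, since 11.1.1.8 protects it. The summaries are descriptive, and Protocol 13.6.7 plans no inference on safety parameters. The case for acting is that the correction costs almost nothing.

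**What to change.** In SAP 8.11.4, limit the 00:00 rule to Day 1 vital-sign records identified as pre-dose by CRF page or planned time point. State that no other untimed Day 1 record may serve as baseline. If no identifiable pre-dose Day 1 value exists, use the Day -1 Baseline visit value. In 2.1.3 or 11.1.1.8, add that for baseline the time rule in 11.1.1.8 takes precedence over the same-day sequence rule.

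With these changes no pattern in the table yields a post-dose baseline. A, D and E give the pre-dose value, as does B when its pre-dose record can be identified. C, and any case where it cannot, gives the Day -1 value.

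The cost is a few words of SAP text and a small programming filter. No new data are needed, because Day -1 vital signs are already scheduled.
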